9.2 Where the Consent Process Will Take Place

Consent will take place via video-conference.

9.3 SOP: Informed Consent Process for Research (HRP-090)

Standard SOP and Summary of Current Guidance on Alternative Informed Consent Procedures for Research Studies Impacted by COVID-19.

For Multi-Site Study: This study will not be initiated until the protocol and informed consent document(s) have been reviewed and approved by a properly constituted Institutional Review Board (IRB) or Independent Ethics Committee (IEC). Each participant (or legal guardian) shall read, understand, and electronically sign an instrument of informed consent prior to performance of any study-specific procedure. It is the responsibility of the investigator to ensure that the participant is made aware of the investigational nature of the treatment and that informed consent is given.

The Investigator is responsible for the retention of the participant log and participant records; although personal information may be reviewed by authorized persons, that information will be treated as strictly confidential and will not be made publicly available. The investigator is also responsible for obtaining participant authorization to access medical records and other applicable

Roswell Park Protocol Number: I 757820

study specific information according to Health Insurance Portability and Accountability Act regulations (where applicable).

This study will be conducted in compliance with all applicable laws and regulations of the state and/or country and institution where the participant is treated. The clinical trial should be conducted in accordance with the ethical principles embodied in the Belmont Report: Ethical Principles and Guidelines for the Protection of Human Subjects of Research, consistent with good clinical practice and the applicable regulatory requirements and according to the guidelines in this protocol, including attached appendices.

10 PROCESS TO DOCUMENT CONSENT IN WRITING

10.1 SOP: Written Documentation of Consent (HRP-091)

We will obtain documentation of consent.

10.2 If Your Research Presents No More Than Minimal Risk of Harm to Subjects and Involves No Procedures for Which Written Documentation of Consent is Normally Required Outside of the Research Context, the IRB Will Generally Waive the Requirement to Obtain Written Documentation of Consent.

N/A.

10.3 Waiver of Consent Documentation

N/A.

For Multi-Site Study: The Investigator (or IRB specified designee) is responsible for obtaining written consent from each participant in accordance with GCP guidelines using the approved informed consent form, before any study specific procedures (including screening procedures) are performed. The informed consent form acknowledges all information that must be given to the participant according to applicable GCP guidelines, including the purpose and nature of the study, the expected efficacy and possible side effects of the treatment(s), and specifying that refusal to participate will not influence further options for therapy. Any additional information that is applicable to the study must also be included. Additional national or institutionally mandated requirements for informed consent must also be adhered to. The participant should also be made aware that by signing the consent form, processing of sensitive clinical trial data and transfer to other countries for further processing is allowed.

The investigator or designee shall provide a copy of the signed consent form to the participant and the signed original shall be maintained in the investigator file. A copy of the signed consent form must be filed in the participant file. At any stage, the participant may withdraw from the study and such a decision will not affect any further treatment options.

11 PROCEDURES INVOLVED

11.1 Study Design

Examine how filter ventilation messaging influences real-world product use, perceptions of and responses to products, and awareness of filter ventilation.

Roswell Park Protocol Number: I 757820

Cigarettes are not smoked in isolation, but in a broader informational context. Thus, the effects of ventilation on responses to product use must be assessed with respect to product communications. We will conduct a field protocol in which various product messaging will be assessed under real-world product use experiences in terms of consumers' ratings of product appeal, risk perceptions, or change cigarette smoking behavior. We hypothesize that messaging will influence filter ventilation awareness and perceptions, but not behavior change.

Filters from these sessions will be used to examine within-cigarette compensatory smoking behaviors (e.g., vent blocking; mouth level exposure).¹¹⁴⁻¹¹⁶

11.2 Treatment

This study will use two types of cigarettes. One set of cigarettes are commercially available Marlboro cigarettes (Philip Morris USA, Richmond, VA), all combustible King size (83mm) cigarettes consisting of filler, filter paper, tipping paper, cigarette paper, tipping glue and seam glue. Specific varieties are listed in the table. Products will be sourced at retail from local outlets.

Alternatively, participants may receive investigational “roll your own” (RYO) cigarettes that will be prepared in the laboratory. These cigarettes will be made to match the commercially available Marlboro cigarettes. These cigarettes will be prepared with conventional tobacco (e.g., Good Stuff) rolled using an automatic rolling machine (e.g., Powermatic III+) and packaged into 20 rod packs. The investigational RYO cigarettes will use ventilated filter tubes (e.g., ~25-37% filter ventilation). The dose of nicotine in these RYO cigarettes will be similar to conventional cigarettes.

Within each pair of products is a nonmenthol and menthol equivalent. Participants who report regularly smoking menthol cigarettes will receive the menthol versions for the study.

Variety	Vent %	Filter length (mm)	Tobacco weight (mg)
Special Blend Smooth Mellow	30.6	27	625.1
Smooth Fresh Menthol	37.6	27	630.8

Additionally, cigarettes will be paired with messaging about filter ventilation. This message will be affixed to the front exterior of each package provided to participants.

- No Message (e.g., unaltered cigarette pack).
- Neutral Message: “Nothing about this product’s color or name means that it will protect a smoker from the health risks of smoking.”
- Compensation Message: “This product has a ventilated filter. Filter vents increase how deeply a smoker inhales without them knowing, which can increase the health risks of smoking.”
- Blocking Message: “This product has a ventilated filter. Be sure not to block the vent holes with your fingers or lips, which can increase the health risks of smoking.”

Roswell Park Protocol Number: I 757820

With these conditions, ‘no message’ serves as a true control (smoking as normal), while the neutral message serves as a control message to determine if added messaging impacts behavior/perceptions, even if that message is not informational. The compensation and blocking messages will determine if added messaging about the health risks of filter ventilation affect behavior/perceptions, and which type of message has the greater impact.

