2.2 Relevant Preliminary Data

The PI ([name]) and the investigative team have extensive experience in examining biobehavioral responses to cigarette design. Pilot research relevant to the current proposal ([name], unpublished) assessed responses to "light" cigarettes and packaging. Participants (N=90) were current smokers whose brand of choice was Marlboro "Lights"/Gold. Using a factorial design, participants were randomized to receive a Marlboro "Lights" cigarette presented in one of three pack conditions 1) text descriptors present; 2) text descriptor removed; and 3) plain (brown) pack. Participants smoked two cigarettes, in counterbalanced order: 1) blocked and 2) unblocked. A significant interaction was observed between pack design and ventilation on measures of smoking *Effect* ($p=0.007$), with the ventilated cigarette producing greater perceived effect as pack descriptors were removed, and *Throat Impact* (a cue for nicotine delivery) ($p=0.039$). Pack design and ventilation also interacted to influence sensory perceptions of irritation, and taste ($p's < 0.017$), with higher ratings seen on plain packs with blocked ventilation.

[figure not shown]

Figure 1. Interaction of filter ventilation and pack descriptor on drug effect and liking measures.

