13 RISKS TO SUBJECTS

13.1 Foreseeable Risks

Answering questionnaires pose none to minimal risk. In the event a question causes any type of distress, information will be provided to identify psychological resources available to the participant. There is no to minimal risk for providing breath samples for measurement of carbon monoxide (CO). When providing materials to participants by mail, delivery confirmation with signature will be used to confirm the correct person receives the materials.

Cigarette smoking.

Since we are using commercially available cigarettes, the side effects of the cigarettes used in this study would be similar to the use of other commercial cigarette products, including those the participants smoke themselves. Participants could experience an increased risk for mouth sores, gum disease and tooth loss, nausea or stomach aches, vomiting, or high blood pressure. Some people who use cigarettes may experience irritation of the mucosal membranes of the upper respiratory tract (i.e., the membranes that line the mouth and throat), but as the participants in this study are already regular users, we do not think that this is likely to occur.

Roswell Park Protocol Number: I 757820

- Rare but Serious Side Effects: Those that occur in less than 5% of persons who use nicotine products.
 - Mouth irritation
 - Severe sore throat
 - Irregular heartbeat or rapid heartbeat
- More common but less Serious Side Effects: Those that occur in less than 10-30% of persons who use nicotine products.
 - Indigestion or heartburn
 - Nausea, vomiting, dizziness, diarrhea, or weakness

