22 STATISTICAL PLAN

22.1 Data Analysis Plan

The analysis of EMA data will be analyzed using a linear mixed model with fixed effects for vent message (product design, color/name), as well as sex and other tobacco product strata (cigarettes only or dual use). The effect of packaging will be tested using a Bonferroni-corrected type-I error rate of 0.008 (0.05/6) to account for all possible pairwise comparisons of packaging types. Data from the field-study (e.g., change in product responses, risk, TNE, aldehyde-DNA adducts) will be analyzed using linear regression with terms in the model for vent message (no message, neutral, compensation, blocking), sex, and other tobacco product use.. Categorical outcomes for the field-study will be analyzed using logistic regression. As exploratory approaches, we will use time-varying effects models (TVEMs) to explore the effect of message condition on smoking behavior (product compliance), craving, risk perception, and quit intention in the EMA data.[191, 192] TVEMs have been used previously to examine treatment effects on craving [193] and relapse.[194] TVEMs will provide daily effect sizes, thereby allowing us to examine whether treatment effects (and relationships with other predictors) change over time (i.e., early vs. later in product switching). Responses at Visit 1 can be treated as time invariant predictors and mCEQ from EMA can be treated as time-varying predictor (and/or outcome) of product use.

Roswell Park Protocol Number: I 757820

We will enroll a total sample size of 300 subjects and assume a 20% drop-out rate with uniform drop-out from Visit 1 to Visit 3. This will result in a sample size of 300 subjects for Visit 1, 270 subjects for the first week of the field study, and 240 subjects for the end of field study. Our sample size was determined to have adequate power for the field study, For the field study, we hypothesize a 25% difference between conditions, corresponding to a 3.9 CPD difference. Assuming a standard deviation of 7.6,[195] a sample size of 240 subjects will provide 95% power to detect a significant difference between ventilation conditions at the 0.05 level and 80% power to detect a significant difference between packaging conditions with a Bonferroni-corrected type-I error rate of 0.008.

mCEQ is scored using an established algorithm.⁹⁶ This results in 3 subscales (Psychological Reward, Relief, Reward) and 2 single items (Aversion, Respiratory sensation). Scores range from 1-7.

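### No rule assigns Marlboro or laboratory-made cigarettes, and product type and menthol are in neither the allocation nor the models: precision is lost, and independence of product from message arm cannot be verified

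*Combined protocol and SAP*

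**What the plan says.** Section 11.2 states: "This study will use two types of cigarettes". One is retail Marlboro, with tabulated ventilation of 30.6% (non-menthol) and 37.6% (menthol). The other is machine-rolled investigational cigarettes "that will be prepared in the laboratory. These cigarettes will be made to match the commercially available Marlboro cigarettes". Their ventilation is given only as an example range: "The investigational RYO cigarettes will use ventilated filter tubes (e.g., ~25-37% filter ventilation". Regular menthol smokers receive the menthol version. No sentence says who receives Marlboro and who receives RYO, at which site or in which period.

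Section 11.3 randomises to one of four messages after consent and then arranges delivery of the cigarettes and other materials. It names no stratification factor. Section 4.1 sets recruitment targets by sex and site, not by product.

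In Section 22.1 the field-study regression has "terms in the model for vent message (no message, neutral, compensation, blocking), sex, and other tobacco product use". The EMA mixed model has the same three factors; its mention of product design and color/name only glosses the message factor. Neither model has a Marlboro/RYO or menthol term, although Section 11.4 collects menthol preference among the baseline covariates.

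Section 13.1 opens its account of smoking risks on a single-product basis: "Since we are using commercially available cigarettes, the side effects of the cigarettes used in this study would be similar".

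**The concern.** The endpoints most exposed are those that describe the cigarette itself. Primary 1 in Section 3 consists largely of product ratings (Duke Sensory Scale, Product Evaluation Scale, Drug Effects, Hedonic Attribute), and some items ask how similar the cigarette is to the usual brand. The baseline product ratings in Session 1 are of the usual brand, so change scores carry the switch to the study cigarette. The topography endpoint is particulate retained on used filters, and the RYO filter tube may differ from the Marlboro filter.

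Menthol follows the participant's own prior use, so it is fixed before randomisation. Marlboro or RYO is different. With no stated rule, and with supply arranged once the message arm is known, randomisation to message does not by itself guarantee that product is independent of arm. Precision is at stake in any case. The validity of the message contrasts is at stake only if product share differs systematically between arms.

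**Working it through.** **Inputs.** Section 22.1 gives a difference of 3.9 cigarettes per day, an SD of 7.6, 240 completers and alpha 0.008 for pairwise message comparisons. Equal allocation (240/4 = 60 per arm) and two-sided tests are assumed, because Section 11.3 states no ratio. The documents give neither the RYO share p nor the product effect g (in within-product SDs), so both are shown over a range.

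**Reference power.** 3.9 / (7.6 × √(2/60)) = 3.9/1.388 = 2.811. The critical value at two-sided 0.008 is 2.652. Power = Φ(2.811 − 2.652) = Φ(0.159) = 0.563. The plan states 80% for this comparison. These inputs give that only at unadjusted two-sided alpha 0.05 (0.803). That gap is a separate matter; 0.563 serves here as the reference with product adjusted for.

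**Case A: product independent of message arm.** There is no bias. A simulation of 40,000 pairs of arms of 60 gives an unadjusted type I error of 0.008 at nominal 0.008. Leaving product out multiplies the variance by 1 + p(1−p)g². For p = 0.5 and g = 0.5 this is 1 + 0.25 × 0.25 = 1.0625, and power is Φ(2.811/√1.0625 − 2.652) = 0.530.

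| p | g | extra variance | power, product omitted |
|---|---|---|---|
| 0.3 | 0.5 | 5% | 0.535 |
| 0.5 | 0.5 | 6% | 0.530 |
| 0.5 | 0.8 | 16% | 0.483 |
| 0.5 | 1.0 | 25% | 0.445 |

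On cigarettes per day, g = 0.5 would be 0.5 × 7.6 = 3.8, nearly the planned effect. The range is therefore better read as an illustration for the rating endpoints, for which the plan gives no SD.

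Chance imbalance is not an additional harm. The SD of the arm difference in RYO share at p = 0.5 is √(2 × 0.25/60) = 0.091. Then 1.96 × 0.091 × 0.5 = 0.089 SD. The ordinary sampling error of the contrast is 1.96 × √(2/60) = 0.358 SD, and (0.089/0.358)² = 0.06, which is the same 6%.

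**Case B: product share differs systematically by arm.** Bias = g × (difference in share). For g = 0.5 and 60 per arm, the simulation gives:

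| RYO share in the two arms | bias (SD) | type I error, nominal 0.008 |
|---|---|---|
| 60% v 40% | 0.10 | 0.017 |
| 70% v 30% | 0.20 | 0.056 |
| 100% v 0% | 0.50 | 0.52 |

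The last row is the extreme case. There product and message coincide, and no model term could separate them.

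**The case against.** A reader might infer that the message effects are already mixed with product differences. The documents do not support that. Message is randomised, and no sentence ties product to arm. Menthol is fixed beforehand and balanced in expectation. Even if RYO is used only at one site or in one period, it is balanced across arms in expectation provided all four messages are randomised there.

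Section 11.2 also points to a modest product effect: the RYO cigarette is meant to match Marlboro, with similar nicotine and overlapping ventilation. The pilot in Section 2.2 cannot be used to argue otherwise. It reports a pack-by-ventilation interaction on irritation and taste, "with higher ratings seen on plain packs with blocked ventilation", but it compared blocked with unblocked vents on one Marlboro product, not commercial with laboratory-made cigarettes.

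A reader might also infer that the neutral and no-message controls mean different things by product, because the neutral text reads "Nothing about this product’s color or name means that it will protect a smoker from the health risks of smoking" and no color or name is described for RYO packs. That rests on silence about those packs. Within either product the contrast remains randomised, and pooling estimates a valid average.

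All of this stands. It does not supply the missing rule. Matching is stated as an aim without a test or tolerance, and supply after randomisation leaves the independence of product and message unverified.

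**Conclusion.** The point holds as a gap in specification and a loss of efficiency, not as demonstrated confounding. If product is independent of message arm, the contrasts are unbiased and the cost is precision: about 6% extra variance, or power of about 0.53 instead of 0.56, at p = 0.5 and g = 0.5. At a full 1.0 SD product difference, power is about 0.45. If product is not independent of arm, the bias is the product effect times the difference in share, for example 0.10 SD at 60% v 40% with g = 0.5. The plan does not exclude this, but contains no evidence of it. All these sizes rest on assumed values of p and g and on 60 per arm. Separately, Section 13.1 argues from commercial cigarettes while Section 11.2 also allows investigational ones. This is an inconsistency to resolve, not evidence of bias.

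**What to change.** - State in Section 11.2 how Marlboro or RYO is assigned, and set it before or independently of the message assignment, for example by balancing the four messages within each product or RYO batch.
- Record the product for every participant. Appendix C already has a product code field.
- Add product type (Marlboro/RYO) and menthol as fixed effects in both Section 22.1 models.
- Analyse filter particulate within product or adjusted for it.
- Report a commercial-pack-only analysis as supportive, noting its smaller sample.
- Reconcile Sections 11.2 and 13.1 on which cigarettes are used.

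The model terms cost about two degrees of freedom and can be added even after enrolment has begun. Stratifying by product crossed with sex and site is not needed: four product versions × two sexes × three sites make 24 cells, or 300/24 = 12.5 participants each, about three per arm. The assignment rule matters more than the model terms, because adjustment cannot repair complete overlap of product and message.

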11.3 Study Procedures

The proposed study is a between-subjects design in which participants will be randomized to 1 of 4 conditions for 2 weeks.

- No Message (e.g., unaltered cigarette pack).
- Neutral Message: “Nothing about this product’s color or name means that it will protect a smoker from the health risks of smoking.”
- Compensation Message: “This product has a ventilated filter. Filter vents increase how deeply a smoker inhales without them knowing, which can increase the health risks of smoking.”
- Blocking Message: “This product has a ventilated filter. Be sure not to block the vent holes with your fingers or lips, which can increase the health risks of smoking.

Data will be collected in three remote video sessions and via EMA conducted over 2 weeks. Each study session is expected to take 0.5 hours. For each condition, active data collection is expected to take no more than 15 minutes. Study materials (cigarettes, CO monitor, containers for cigarette filter collection, scales) will be mailed to, delivered, or picked up by participants. Session 1 will involve confirmation of receipt of study materials, questionnaires, and training on procedures. Then, participants will track their product use via EMA app (REDCap) for 2 weeks, with two remote sessions via videoconference for additional questionnaires.

Informed Consent. An initial videoconferencing session will be used for informed consent. Consent will be obtained through the REDCap (Research Electronic Data Capture) system used for data collection. REDCap is a secure web-based application that supports data capture and management for research studies. The Investigator and Research Associate will design the study specific consent and upload the most recent CRS versions to the REDCap system. A secure link will be sent to each participant prior to the start time of the study. Research staff will guide the participant form, provide time to read the consent, and answer any questions. Participants and staff will be able to electronically sign, data, and submit the consent in real-time. Once the consent is submitted, it is automatically saved on RPCI protected servers. Access to this folder is restricted to authorized users. Standard protocols for data encryption (via Credant) when using laptops and USB drives will be followed.

In the event of REDCap being inaccessible for a study visit, .pdf files or paper copies of the consent will be provided to the participants and the participants will be able to sign and return or submit a photo of the signed copy.

The participant will then be randomized to 1 of 4 message conditions (No message, Neutral message, Compensation message, Blocking message) and arrangements will be made to mail, deliver, or have participants pick up study materials (study cigarettes with pack messages, CO

Roswell Park Protocol Number: I 757820

monitor, scales, butt collection materials, shipping materials, etc.). Participants will be provided with two weeks of materials.

Session 1. Session 1 will occur upon receipt of study materials by the participant. Participants will complete a baseline intake questionnaire including smoking and tobacco use history, nicotine dependence scales, SCQ, TRIRISK, delay discounting, respiratory symptoms, and knowledge, attitudes, and beliefs about filter vents. In addition, participants complete questionnaires on message perceptions (response to messaging, health risk, purchase intention) for all pack messages. Questionnaires also will be used to get baseline assessments of the user's usual brand of cigarettes (Duke Sensory Scale, Product Evaluation Scale, Hedonic Attribute Scale). Participants will be instructed to record each smoking event using the EMA app provided (described in more detail below) and to retain all spent cigarette butts and unused product. Participants will be informed that they are free to use other tobacco products (though they will not be provided as part of the study), and that these should be recorded using EMA. Participants will be provided for cigarettes for a total of two weeks, with the amount determined by normal self-reported weekly consumption rounded to nearest whole pack.

Remote Data Collection. Participants will complete the two-week study remotely using EMA methods. At the conclusion of Session 1, participants will be trained to record their assigned product use via EMA for data collection. Specifically, participants will respond to 5 scheduled questionnaires daily. These questionnaires are designed to assess product consumption, context of use (e.g., location, social situation), and subjective responses (e.g., withdrawal, product evaluation, message attention - more details on surveys provided below). Participants will be prompted to measure their exhaled-air CO level and product weight twice each day using a personal monitor provided to them. Participants will also retain all spent cigarette butts and unused products throughout the two weeks.

Day 3 Check-in: Research assistants will monitor EMA data to ensure the participant is compliant with study procedures. Participants will send a secure text message (via Twilio) or arrange a phone call to discuss the participant's compliance in the initial days of data collection. Participants that are not responding to prompts will be retrained to ensure they understand procedures and warned that compliance must increase to continue participating in the study.

Session 2 will take place one week later (\pm 2 days) via remote videoconference using an institution-approved software with a password protected meeting (e.g., WebEx, Microsoft Teams, Zoom). The Session 2 videoconference will include the completion of questionnaires on vent awareness, product evaluation, and readiness to quit (similar to Visit 1). Participants will again be asked on message perceptions, but only in relation to their randomly assigned condition.

Session 3 will take place one week later (\pm 2 days) via remote videoconference. The same questionnaires from Session 2 will be administered again. Laboratory staff will guide participants to place all materials (retained filter butts, unused products, unsigned payment receipts) in the provided shipping box. Arrangements will be made for the participant to return materials or for research staff to pick up materials. Participants will be paid for Visit 3 upon verification of returned study materials.

